APPENDIX B STRONG INDUCERS OF CYP ISOENZYMES

CYP Enzymes	Medications
CYP3A4/3A5	Avasimibe, carbamazepine, phenytoin, rifampin, St. John's wort
CYP2B6, CYP2C9, CYP2C19	Currently no known inducers

Please note the following: This is not an exhaustive list. For an updated list, refer to the following link:
<http://www.fda.gov/Drugs/DevelopmentApprovalProcess/DevelopmentResources/DrugInteractionsLabeling/ucm080499.htm>.

List of Abbreviations

6MWT	6-Minute Walk Test
AE	Adverse Event
ALT	Alanine Aminotransferase
ANCOVA	Analysis of Covariance
AST	Aspartate Aminotransferase
ATAQ	A Tool to Assess Quality of Life
ATC	Anatomical Therapeutic Chemical
AUC	Area Under the Curve
BMI	Body Mass Index
BUN	Blood Urea Nitrogen
CI	Confidence Interval
CPET	Cardiopulmonary Exercise Test
CRF	Case Report Form
CS	Clinically Significant
CSR	Clinical Study Report
CTCAE	Common Terminology Criteria for Adverse Events
DBP	Diastolic Blood Pressure
DLco	Diffusing Capacity of the Lung for Carbon Monoxide
ECG	Electrocardiogram
eCRF	Electronic Case Report Form
ETCO2	End Tidal Carbon Dioxide
ETO2	End Tidal Oxygen
FEV1	Forced Expiratory Volume in 1 second
FVC	Forced Vital Capacity
GGT	Gamma Glutamyl-transferase
HR	Heart Rate
ICH	International Conference on Harmonisation
INR	International Normalized Ratio
IQR	Interquartile Range
IPF	Idiopathic Pulmonary Fibrosis
IxRS	Interactive Response System
LactThresh	Lactic Acid Threshold
LFT	Liver Function Tests
MedDRA	Medical Dictionary for Regulatory Activities
NCS	Not clinically significant
PDF	Portable Document Format
PK	Pharmacokinetics
PP	Per-protocol
PPT	Partial Prothrombin Time
PR	Pulse Rate
PRO	Patient-Reported Outcomes

PT	Preferred Term
RBC	Red Blood Cells
RER	Respiratory Exchange Ratio
RR	Respiratory Rate
RTF	Rich Text Format
SAE	Serious Adverse Event
SAP	Statistical Analysis Plan
SBP	Systolic Blood Pressure
SD	Standard Deviation
SDC	Statistics and Data Corporation, Incorporated
SGRQ	Saint George's Respiratory Questionnaire
SMC	Safety Monitoring Committee
SOC	System Organ Class
SpO2	Peripheral Oxygen Saturation
SUSAR	Suspected Unexpected Serious Adverse Reaction
TEAE	Treatment-Emergent Adverse Event
TIBC	Total Iron Binding Capacity
TVOL	Tidal Volume
UCSD	University of California San Diego
VAS	Visual Analog Scale
VentThrsh	Ventilatory Threshold
VCO2	Carbon Dioxide Production
VO2	Oxygen Production
WBC	White Blood Cells
WCT	Worldwide Clinical Trials
WHO DDE	World Health Organization Drug Dictionary Enhanced

1. Introduction

The purpose of this statistical analysis plan (SAP) is to describe the planned analyses and reporting for protocol GBT440-006, version Amendment 3, dated December 21, 2016.

This SAP is being written with due consideration of the recommendations outlined in the most recent International Conference on Harmonization (ICH) E9 Guideline entitled Guidance for Industry: Statistical Principles for Clinical Trials and the most recent ICH E3 Guideline, entitled Guidance for Industry: Structure and Content of Clinical Study Reports.

This SAP describes the data that will be analyzed and the subject characteristics, efficacy, and safety assessments that will be evaluated. This SAP provides details of the specific statistical methods that will be used. The statistical analysis methods presented in this document will supersede the statistical analysis methods described in the clinical protocol. If additional analyses are required to supplement the planned analyses described in this SAP they may be completed and will be identified in the clinical study report (CSR).

Planned pharmacokinetic (PK) analyses will be described in a separate analysis plan.

2. Study Objectives

Primary Objective:

To evaluate the safety and tolerability of multiple doses of GBT440 administered to subjects with IPF.

Secondary Objectives:

- To evaluate the effect of GBT440 on oxygen saturation at Days 15 and 28 compared to baseline during the 6-minute walk testing (6MWT).
- To evaluate the pharmacokinetic (PK) parameters of GBT440 in plasma and whole blood.

Exploratory Objectives:

- To evaluate the effect of GBT440 on distance walked during the 6MWT at Days 15 and 28 compared to baseline.
- To evaluate the effect of GBT440 on IPF-related symptoms using patient reported outcomes (PROs) at Day 28 compared to baseline.
- To evaluate the effect of GBT440 on cardiopulmonary exercise testing (CPET) parameters at Day 29 compared to baseline.
- To evaluate pulmonary function, including assessment of spirometry and Diffusing Capacity of the Lung for Carbon Monoxide (DLco) at Day 28 compared to baseline.

- To evaluate the PK-PD relationship of GBT440 at Days 15 and 28 compared to baseline.

3. Study Endpoints

3.1 Primary Endpoint

The primary endpoint is treatment-emergent adverse events (TEAE) and tolerability.

3.2 Secondary Endpoints

- Change and percentage change from baseline in resting peripheral oxygen saturation (SpO₂) at Days 15 and 28 measured prior to beginning the 6MWT.
- Change and percentage change from baseline in end-of-6MWT SpO₂ at Days 15 and 28.
- Change and percentage change from baseline in lowest SpO₂ value measured during the 6MWT at Days 15 and 28.
- Pharmacokinetic (PK) parameters of GBT440 in plasma and whole blood, including but not limited to maximum concentration (C_{max}), minimum concentration (C_{min}) at steady state in GBT440 treated subjects.

3.3 Exploratory Endpoints

- Change and percentage change from baseline in distance walked during the 6MWT at Days 15 and 28.
- Time to first SpO₂ < 88% that is sustained for at least 10 seconds during the 6MWT at Days 15 and 28.
- Area under the SpO₂ curve (AUC) during the 6MWT measured at baseline, Day 15 and Day 28.
- Change from baseline in PRO scores using Saint George's Respiratory Questionnaire (SGRQ), University of California, San Diego (UCSD) Shortness of Breath Questionnaire, A Tool to Assess Quality of Life (ATAQ) in IPF (only subjects enrolled in Part B), and the Borg Scale of Perceived Exertion questionnaires and cough visual analog scale (VAS) at Days 15 and 28.
- Change and percentage change from baseline in cardiopulmonary exercise testing parameters at Day 29.
- Change and percentage change from baseline in lung function, including forced vital capacity (FVC) and DLco at Day 28.
- PK/PD relationship in subjects receiving GBT440 from Baseline to Days 15 and 28

3.4 Statistical Hypotheses

This phase 2 study is designed to evaluate the safety and tolerability of multiple doses of GBT440 administered to subjects with IPF. No formal hypotheses are specified for this study.

4. General Study Design

This study is a randomized, placebo-controlled trial that will be conducted in two parts. Together, Parts A and B will provide safety and efficacy data across a range of GBT440 doses that are expected to improve oxygen saturation in the enrolled subjects.

- In Part A (Figure 1), eligible IPF subjects will be randomized 1:1:1 to receive GBT440 900 mg (n = 6) or 600 mg (n = 6), or placebo (n = 6) administered orally as 300 mg capsules once daily for 28 days. The study site, subjects, CRO statistician and Sponsor will be blinded to study treatment.
- In Part B (Figure 2), eligible IPF subjects will be randomized 3:1:1 to receive GBT440 1500 mg (n = 9) or 600 mg (n = 3), or placebo (n = 3) administered orally as 300 mg capsules once daily for 28 days in which the study site and subjects are blinded to study treatment. The Sponsor and CRO statistician will be unblinded to study treatment.

Subjects on a stable dose of pirfenidone or nintedanib and/or N-acetyl cysteine are eligible for entry into the study.

After the Screening visit, the study includes the following study periods:

- Treatment period (28 days): subjects will be randomized (1:1:1) to one of three treatment groups in Part A and randomized (3:1:1) to one of three treatment groups in Part B; subjects will receive:

Part A:

- Group 1: GBT440 900 mg; three 300 mg GBT440 capsules, daily orally.
- Group 2: GBT440 600 mg; two 300 mg GBT440 capsules and one placebo capsule, daily orally.
- Group 3: Placebo: three placebo capsules, daily orally.

Part B:

- Group 1: GBT440 1500 mg; five, 300 mg GBT440 capsules, daily orally.
 - Group 2: GBT440 600 mg; two 300 mg GBT440 capsules and three placebo capsule, daily orally.
 - Group 3: Placebo: five placebo capsules, daily orally.
- Safety follow-up (30 days): safety will be assessed for at least 5 half-lives after the last dose of GBT440.

Figure 1 Study Design – Part A

[figure not shown]
[figure not shown]

Figure 2 Study Design – Part B

Subjects who do not complete at least 10 days of dosing for reasons unrelated to toxicity may be replaced.

In Part A, two unblinded interim analyses of the primary and secondary endpoints are planned: i) when approximately 9 subjects have completed their Day 28 study visit and ii) when approximately 18 subjects have completed their Day 15 study visit.

A Safety Monitoring Committee (SMC) is planned to review all safety data on an ongoing basis throughout the study (refer to Protocol Section 10.1). If the SMC does not identify any clinically

significant safety concerns in Part A, following review of data from approximately 18 subjects who have completed Day 15, the Sponsor will initiate Part B of the study, and randomize up to an additional 15 subjects to the three study treatment arms to better characterize the safety, tolerability, and potential treatment response of GBT440 in subjects with IPF.

In the eventuality that one treatment arm is discontinued, subjects may be randomized 1:1 to the remaining study drug treatment group or placebo. Therefore, the trial size is approximately 33 subjects.

The end of the study is defined as the date when the last subject completes the last visit, which is expected to occur approximately 58 days after the last subject is randomized.

5. Schedule of Visits and Assessments

The schedule of visits and assessments and PK sampling timepoints are provided below.

5.1 Schedule of Assessments

Study Day (Window)	Screening ^a		Treatment Period					Follow-up Visits	
	Day -21 to Day -1	Day 1	Day 2	Day 8 (+/- 2)	Day 15 (+/- 2)	Day 28 (+/- 2)	Day 29 (+3)	Day 45 ^b (+/- 3)	Day 58 (+/- 3)
Visit	1	2	3	4	5	6	7	8	9
Informed Consent ^c	X								
Eligibility Assessment	X	X							
Demographic data	X	X ^d							
Medical History and baseline conditions		X ^d							
Concomitant Medications	X	X	X	X	X	X	X	X	X
Complete Physical Examination ^e	X								X
Limited Physical Examination ^f		X		X	X	X	X	X	
Height	X								
Weight	X					X			
Vital Signs ^g	X	X	X	X	X	X	X	X	X
SpO ₂ ^h	X	X	X	X	X	X	X	X	X
ECG (12-lead) ⁱ	X			X	X	X		X	X
Adverse Events ^j	X ^j	X	X	X	X	X	X	X	X
Serum Pregnancy Test (females only) ^k	X								
Urine Pregnancy Test (females only) ^l				X	X	X		X	X
Hematology	X			X	X	X		X	X
Serum Chemistry	X			X	X	X		X	X
Urinalysis	X				X	X		X	X
Coagulation Panel (PT, PTT, INR)	X					X			
Serum Erythropoietin	X					X		X	X
Serology (Hepatitis A, B, C, and HIV)	X								
PK Blood Samples ^m		X	X	X	X	X		X	X
Spirometry and DL _{CO}	X					X			X
6-Minute Walk Test ⁿ	X ⁿ				X	X			X
Cardiopulmonary Exercise Testing ⁿ			X				X		
Randomization (IxRS)		X							
Study Drug Dispensing to Subject ^o			X	X	X				
Study Drug Administration at site ^p		X	X	X	X	X			
St. George's Respiratory Questionnaire ^q		X		X	X	X		X	X

UCSD Shortness of Breath Questionnaire ^q		X		X	X	X		X	X
ATAQ-IPF Symptoms ^q		X		X	X	X		X	X
ATAQ-Impacts ^q		X		X	X	X		X	X
End of Study Questionnaire ^r									X
Cough Visual Analog Scale ^q		X		X	X	X		X	X

Abbreviations: ATAQ = A Tool to Assess Quality of Life; DLco = lung diffusing capacity measured using carbon monoxide; ECG = electrocardiogram; HIV = human immunodeficiency virus; INR = international normalized ratio; PK = pharmacokinetic; PRO = patient reported outcome; PT = prothrombin time; PTT = partial thromboplastin time; SGRQ = St. George’s Respiratory Questionnaire, SpO₂ = oxygen saturation measured by pulse oximetry; UCSD = University of California San Diego.

Note: All assessments should be performed within the number of days (Window) as indicated for each scheduled visit day. All assessments should be performed prior to receiving study drug during the treatment period unless otherwise indicated. SGRQ, UCSD, Cough VAS should be performed before all other non-PRO assessments, followed by 12-lead ECG and then vital sign assessments

- ^a All screening evaluations must be completed and reviewed prior to Day 1 (Visit 2) to confirm the subject meets all eligibility criteria prior to randomization to the treatment period. In cases when the screening 6MWT is done more than 7 days prior to Visit 2, it must be repeated, up and through Day 1, prior to any Day 1 assessments.
- ^b All subjects who discontinue study or study drug prior to study completion, and who are unwilling or unable to complete the remaining scheduled visits, should return to the study site to complete all Day 45 (Visit 8) assessments (refer to Protocol Section 6).
- ^c Written informed consent must be obtained and documented prior to performing any study-specific screening procedure.
- ^d Demographics, medical history and baseline conditions obtained at screening should be reviewed again at this visit and any changes since screening updated in the eCRF.
- ^e Includes evaluation of the head, eyes, ears, nose and throat and cardiovascular, respiratory, musculoskeletal, gastrointestinal, neurological, dermatologic systems. No rectal or pelvic examination is required. Record any observed abnormalities in the eCRF. At subsequent visits record new or worsened clinically significant findings on the eCRF
- ^f Perform a limited, symptom-directed examination as clinically indicated. Record new or worsened clinically significant findings in the eCRF.
- ^g Includes heart rate, respiratory rate, systolic and diastolic blood pressure and temperature measured whilst in a semi-recumbent or supine position and resting for at least 5 minutes.
- ^h Performed while the subject is seated and resting for at least 5 minutes.
- ⁱ Perform 12-lead ECG in triplicate; three separate tracings with approximately 1 minute between each tracing, after resting in a semi-recumbent or supine position for at least 5 minutes.
- ^j After informed consent but prior to randomization only serious adverse events (SAEs) resulting from a protocol-mandated intervention should be reported. After randomization all adverse events will be reported until study completion (Day 58).
- ^k Performed for all female patients who are not post-menopausal or surgically sterile
- ^l If a urine pregnancy test is positive the result must be confirmed with a serum pregnancy test.
- ^m PK blood samples during the treatment period should be collected on Days 1 and 28: pre-dose, and 2 hours post dose (+/- 15 minutes); Day 2: 24 hours (+/- 2 hours) after the Day-1 dose *and* prior to receiving the Day-2 dose; Days 8 & 15: pre-dose only. Also see Protocol Section 5.6.
- ⁿ Instructions for per-protocol performance of the 6-minute walk (and Borg dyspnea scale) and cardio-pulmonary exercise tests are provided in the procedure manual. Note: The baseline 6MWT performed during screening must be performed within 7 days of the Day-1 visit.
- ^o An unblinded study pharmacist will prepare daily doses of study drug, dispensed into 30 mL high-density polyethylene (HDPE) bottles. Each bottle (or dose) is packaged individually with 3 capsules of active or placebo or both specific to each subject’s assigned treatment group. Subjects who have their dose modified during the study must return to the site to have the modified dose of study drug dispensed by the unblinded pharmacist.
- ^p Subjects should not administer study drug on the morning of these study visits. Study drug will be administered by the study staff after completion of all pre-dose assessments.
- ^q The SGRQ, ATAQ, and UCSD questionnaires and cough VAS should be self-administered by the subject, using the paper forms provided by the Sponsor prior to all other non-PRO assessments and before the patient receives any disease-status information during that assessment. ATAQ questionnaires should be administered to subjects enrolled in Part b of the study.
- ^r The End of Study Questionnaire should be administered to subjects enrolled in Part B of the study.

6. Study Treatments

The study drug is GBT440 300 mg capsules or placebo.

Subjects randomized to the following treatment groups in Part A will receive:

- GBT440 900 mg -- 3 GBT440 300 mg capsules
- GBT440 600 mg -- 2 GBT440 300 mg capsules and 1 placebo capsule.
- Placebo -- 3 placebo capsules.

Subjects randomized to the following treatment groups in Part B will receive:

- GBT440 1500 mg -- 5 GBT440 300 mg capsules
- GBT440 600 mg -- 2 GBT440 300 mg capsules and 3 placebo capsules.
- Placebo -- 5 placebo capsules.

Study drug is to be dosed orally once daily for a total of 28 days.

6.1 Method of Assigning Subjects to Treatment Groups

Subject randomization will be carried out centrally through an IxRS. Eligible subjects in Part A will be randomized 1:1:1 to receive 900 mg GBT440, 600 mg GBT440, or Placebo. Eligible subjects in Part B will be randomized 3:1:1 to receive 1500 mg GBT440, 600 mg GBT440, or placebo respectively.

The randomization will be stratified by background IPF therapy (pirfenidone/nintedanib or no pirfenidone/nintedanib) use at the time of entry into the study.

6.2 Dose Modifications and Adjustments

Modification of study drug dosing may be considered if, in the opinion of the study Investigator, an AE may be related to study drug and it would be unsafe for the subject to continue receiving their current dose of study drug.

Dose adjustments may be initiated by the Investigator based on their assessment of the associated AE severity and overall subject safety and in discussion with the Sponsor's Medical Director.

The Investigator, in discussion with the Sponsor's Medical Director, may choose to:

- Change dosing frequency, to one capsule 3 times per day
- Reduce the total daily dose

A reduction in dose should be by one active study drug capsule. Dose reductions will require the subject to return to the study site for the unblinded pharmacist to dispense new study drug capsules. Subjects in Part A will continue to take 3 capsules per day. Subjects in Part B will continue to take 5 capsules per day.

A second dose reduction by one active study drug capsule may be initiated if deemed necessary by the Investigator and based on a safety assessment of the subject. The timing of the second dose reduction will be based on the Investigator's clinical assessment and in discussion with the Sponsor's Medical Director.

The Investigator must make every effort to restart the dosing regimen assigned to the subject at randomization when, in the investigator's opinion, it is safe to do so.

6.3 Blinding and Unblinding

An independent biostatistician who is not otherwise involved in the trial will generate the randomized study drug assignment list for Part A of the study. The subject, study team, Investigators, and study staff will be blinded during the randomization process and throughout the duration of the study. The Sponsor and CRO statistician will be unblinded to the treatment assignments when a minimum of 18 treated subjects in Part A complete at least 28 days of study. Sponsor representatives not involved in the conduct of the study will have access to unblinded treatment data throughout the conduct of the study.

The CRO statistician will generate the randomized study drug assignment list for Part B of the study. The Investigators, study staff, and CRO data manager will remain blinded to treatment assignments in Part B of the study. The Sponsor and CRO statistician will not be blinded to treatment assignments in Part B of the study.

The randomization lists will reside on a secure server to which members of the study team will not have access until the study is unblinded per the protocol.

If at any time during the study a decision about a subject's medical condition requires knowledge of the treatment assignment, the study blind may be broken (through the interactive response system [IxRS]) for that specific subject only. If, in the opinion of the Investigator, there is no impact on subject safety, the Investigator is encouraged to contact the Sponsor's Medical Director prior to unblinding. The reason for unblinding must be documented in the appropriate section of the case report form (eCRF).

The SMC must be informed by the Sponsor's Medical Director of any case of unblinding. Additionally, the SMC may unblind any individual treatment assignment for further safety evaluation at their discretion.

7. Sample Size and Power Considerations

The sample size in this study was not selected based on statistical considerations but to determine preliminary safety, tolerability, PK, laboratory and clinical effects of GBT440 in IPF subjects.

The study will enroll approximately 33 subjects: approximately 18 subjects in Part A and approximately 15 subjects in Part B.

8. Data Preparation

All reported study data will be recorded on the eCRFs supplied by Worldwide Clinical Trials (WCT) using eClincialOS™, version 2016.5.0. All data collected on the eCRF will be mapped from the clinical database to the appropriate Clinical Data Interchange Standards Consortium (CDISC) Study Data Tabulation Model (SDTM) domains (Implementation Guide version 3.2). Analysis datasets will be mapped to the CDISC analysis data model (ADaM) using the ADaM Implementation Guide (version 1.1) for all data presented in summary tables and figures. Listings will generated from SDTM domains or ADaM datasets as appropriate.

The final analyses for this study will be carried out after the following have occurred:

- All data management requirements are met according to WCT standard operating procedures, including data entry, performance of edit and validation checks, documentation and resolution of data queries, and database lock with written authorization provided by appropriate WCT and Sponsor personnel;
- Protocol deviations have been identified and status defined (major/minor deviations); and
- Analysis populations have been determined

9. Analysis Populations

9.1 Safety Population

All subjects who receive any amount of study drug will be included in the Safety population. Subjects will be analyzed based on study drug received. This is the primary population for all safety analyses performed for this study.

9.2 Efficacy-Evaluable Population

All randomized subjects who received at least 14 days of study drug treatment will be included in the Efficacy-Evaluable population. The Efficacy-Evaluable population will be used for analysis of all secondary and exploratory efficacy endpoints, and subjects will be analyzed as treated.

9.3 PK Population

All subjects who receive investigational treatment and provide adequate data to evaluate the relevant PK parameter will be included in the PK population. The PK population will not be used for analyses described in this statistical analysis plan (SAP).

10. General Statistical Considerations

10.1 Missing or Inconclusive Data Handling

If only a partial date is available and is required for a calculation of whether a medication is concomitant or an AE is treatment-emergent, the following standards will be applied:

10.1.1 Start dates (e.g., AE onset date or start date of medication)

- For missing start day only - Day will be imputed as the first day of the month (i.e., 1) with the following exception: if the partial date falls in the same month and year as the date being used in the calculation (e.g., first dose date, informed consent date), then the partial date will be imputed to equal the date being used for the calculation.
- For missing start day and month - Day and month will be imputed as the first day of the year (i.e., 1 January) with the following exception: if the partial date falls in the same year as the date being used in the calculation (e.g., first dose date, informed consent date), then the partial date will be imputed to equal the date being used for the calculation.

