5.3.1. Medical History and Demographic Data

Medical history includes clinically significant diseases, surgeries, cancer history (including prior cancer therapies and procedures), inflammatory/autoimmune disease, smoking history, use of alcohol and drugs of abuse within the previous year, and IPF-associated conditions including but not limited to pulmonary hypertension, familial IPF and gastroesophageal reflux disease. Medical conditions that are a result of side effects from concomitant medications should be clearly defined and entered into the eCRF.

Any medical condition present at baseline should be followed during the study and a change from the baseline status (intensity or frequency) should be reported as an adverse event if deemed clinically significant by the investigator (refer to [Section 10](#)).

All concomitant medications (e.g., prescription drugs, over-the-counter drugs, herbal/homeopathic remedies, nutritional supplements) used by the patient within 30 days prior to the Screening visit should be entered on the Concomitant Medications eCRF. A start date should be entered for all medication items entered into the Concomitant Medications eCRF, including those medications used chronically.

Demographic data will include age (date of birth), sex, and self-reported race/ethnicity.

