10.1.2 Stop dates (e.g., AE resolution date or stop date of medication)

- For missing stop day only - Day will be imputed as the last day of the month (i.e., 28, 29, 30, or 31)
- For missing stop day and month - Day and month will be imputed as the last day of the year (i.e., 31 December)

Any partial dates will be displayed in data listings without imputation of missing days and/or months (e.g., MAR2011, 2009). No other imputation of missing data will be performed.

No imputation methods will be used for analysis of missing efficacy data in this study.

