13.2 Prior and Concomitant Medications

Concomitant medications will be coded using the World Health Organization (WHO) Drug Dictionary (Enhanced B2, March, 2016) and summarized to the therapeutic drug class (Anatomical Therapeutic Chemical (ATC) 4 classification) and preferred name. Medications with missing ATC codes will be classified as “uncoded”.

Concomitant medications are defined as those medications having been taken 1) prior to initiation of study drug administration and continuing for any period of time following the first administration of study drug or 2) at any time following the first administration of study drug and within 30 days of last dose.

14. Study Drug Administration, Extent of Exposure, and Dosing Compliance

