15.1 Analyses of Treatment-emergent Adverse Events and Serious Adverse Events

TEAEs are defined as any event that occurs or worsens on or after the first dose of study drug and within 30 days after the last dose. Adverse events recorded in the eCRF which began prior to first dose of study drug will not be included in the summary tables but will be included in the AE data listings.

Adverse events reported for subjects participating in this study will be graded using the National Cancer Institute's (NCI) Common Terminology Criteria for Adverse Events (CTCAE), version 4.03. All AEs will be coded using the using MedDRA, version 19.0.

An overall summary will be presented that includes the number of TEAEs and the number and percentage of subjects who experienced at least one TEAE, by study drug and all GBT440. This summary will also include the number of Grade 3 or greater TEAEs, the number and percentage of subjects with at least 1 TEAE ≥ Grade 3, the number of possibly/probably related TEAEs, the number and percentage of subjects with at least 1 possibly/probably related TEAE, the number of serious adverse events (SAEs), the number and percentage of subjects with at least 1 SAE, the number of TEAEs leading to study drug discontinuation, the number and percentage of subjects who discontinued study drug due to TEAEs, and the number and percentage of deaths.

Additional summaries of TEAEs by study drug and all GBT440 will include the following:

- Incidence of TEAEs by SOC and PT

- Incidence of TEAEs by SOC and PT by antifibrotic use
- Incidence of TEAEs of Special Interest by SOC and PT
 - (If less than 5 events occur in each treatment group, then only a listing will be created)
- Incidence of TEAEs by SOC, PT, and Maximum Severity
- Incidence of TEAEs by SOC, PT, and Maximum Severity by antifibrotic use
- Incidence of TEAEs Resulting in Discontinuation of Study Drug
- Incidence of TEAEs Possibly/Probably Related to Study Drug
 - (If less than 5 events occur in each treatment group, then only listing will be created)
- Incidence of SAEs

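### The SAP's partial start-date rule ignores the stop date, so an adverse event that ended before first dose can, read literally, be counted as treatment-emergent (minor)

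*SAP*

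**What the plan says.** SAP 10.1 applies its date rules when a partial date "is required for a calculation of whether a medication is concomitant or an AE is treatment-emergent, the following standards will be applied".

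SAP 10.1.1 has two bullets for start dates. The default is the first day of the known month, or 1 January of the known year. Each bullet has one exception:

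- Day missing: the trigger is "if the partial date falls in the same month and year as the date being used in the calculation (e.g., first dose date, informed consent".
- Day and month missing: the trigger is "if the partial date falls in the same year as the date being used in the calculation (e.g., first dose date, informed consent date".

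In both cases the consequence is the same: "then the partial date will be imputed to equal the date being used for the calculation".

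SAP 10.1.2 completes partial stop dates, for example "For missing stop day only - Day will be imputed as the last day of the month". It also says that listings show partial dates without imputation. It puts no limit on the imputed start.

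SAP 15.1 gives the outcome definition: "TEAEs are defined as any event that occurs or worsens on or after the first dose of study drug", with a limit of 30 days after the last dose. Adverse events that began before first dose stay in the listings but are left out of the summary tables. The stop date is not mentioned.

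SAP 13.2 defines a concomitant medicine differently. Either it was taken before dosing and continued for some time after first dose, or it was taken "at any time following the first administration of study drug and within 30 days of last dose".

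**The concern.** Moving an uncertain onset to the first-dose date is a sensible conservative rule when timing is unknown. It is not sensible when the same record carries a stop date before first dose, because the event must then have begun before dosing. The exception in SAP 10.1.1 is triggered by the month or year alone, so it can produce a start later than the stop. The onset-based definition in SAP 15.1 then accepts the record as treatment-emergent.

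TEAEs are part of the primary endpoint, the arms are small, and the summaries are percentages of subjects. The tables and listings could also disagree: a listing would show an event ending before Day 1 while the table counts it as treatment-emergent.

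**Working it through.** The plan gives no figure on this point, so there is none to reproduce. The check applies the rules to test records and then sizes the effect.

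**Step 1: test records.** Assume first dose on 20 March 2017 and last dose 27 days later, on 16 April. The TEAE window is then 20 March to 16 May (16 April + 30 days).

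| Recorded start | Stop | Start under SAP 10.1.1 | Start after stop? | TEAE as written | TEAE with a stop-date check |
|---|---|---|---|---|---|
| MAR2017 | 12 Mar 2017 | 20 Mar 2017 | Yes, by 8 days | Yes | No |
| 2017 | 5 Feb 2017 | 20 Mar 2017 | Yes | Yes | No |
| FEB2017 | 12 Mar 2017 | 1 Feb 2017 | No | No | No |
| MAR2017 | MAR2017, imputed 31 Mar | 20 Mar 2017 | No | Yes | Yes |

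Rows 1 and 2 show the fault. Row 2 tests the logic only: a 21-day screening period before 20 March opens on 27 February, so an adverse event ending on 5 February would not normally be on the form. Row 4 shows that a stop-date check leaves the conservative rule in place where timing is unknown.

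**Step 2: the same records as medicines.** In rows 1 and 2 the medicine stopped before first dose. It did not continue past first dose and was not taken after it, so it meets neither limb of SAP 13.2. It would be classed as concomitant only if the program tested the imputed start and ignored the stop.

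**Step 3: how often the exception would catch an affected record.** Take only adverse events that start in the 21 days before first dose, end before it, and have a partial start with a complete stop date. Assume that onset is uniform over the eligible days and first dose is uniform over a 365-day year. Let k be the number of days from onset to first dose. An event whose stop falls D days after its onset ends before dosing only if k runs from D + 1 to 21 (from 1 when D = 0), so the mean is (D + 22)/2. A month of length L contains L − k first-dose dates whose onset is in the same month. Summing over 12 months:

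- Day missing: share = (365 − 12 × mean k)/365
- Day and month missing: share = (365 − mean k)/365

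| D (days) | Mean k | Day missing | Day and month missing |
|---|---|---|---|
| 0 | 11 | 233/365 = 63.8% | 354/365 = 97.0% |
| 3 | 12.5 | 215/365 = 58.9% | 352.5/365 = 96.6% |
| 7 | 14.5 | 191/365 = 52.3% | 350.5/365 = 96.0% |
| 14 | 18 | 149/365 = 40.8% | 347/365 = 95.1% |

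A day-by-day enumeration gives the same values. They are shares of affected records only, not of all adverse events.

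**Step 4: effect of one record.** Planned arm sizes come from SAP 4, pooled as in SAP 10.3: 900 mg, 6; 1500 mg, 9; 600 mg, 6 + 3 = 9; placebo, 6 + 3 = 9. If the subject has no other TEAE, one false TEAE adds:

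- 1/9 = 11.1 points in an arm of 9;
- 1/6 = 16.7 points in the 900 mg arm;
- 1/24 = 4.2 points in the all-GBT440 column (6 + 9 + 9 = 24).

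If the subject has a genuine TEAE, the overall incidence does not move. Only the event count and the relevant system organ class or preferred-term row could change.

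**Step 5: how many such records can exist.** Protocol 10.2 restricts reporting before randomization to SAEs and adverse events caused by protocol interventions. Footnote j to the schedule, in both documents, is narrower: only SAEs caused by a protocol-mandated intervention. An affected record must also have a partial start and a stop date before dosing.

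**The case against.** The strongest reply is that the rule is never reached. SAP 10.1 applies it only when a partial date is needed for the classification. If the stop date precedes first dose, the class is already known. SAP 15.1 also leaves out of the tables events that began before first dose, and an event that ended before dosing must have begun before it. This is a reasonable reading, and a careful programmer might adopt it. But the SAP does not say that a stop date settles the class, and a derivation based on onset needs a start date. The wording permits both outcomes.

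Several points on scale do stand. Exposure is very small, and a year-only onset for an event seen during screening is hard to imagine. SAP 8 requires validation checks and query resolution before lock, which should complete some dates. SAP 3.4 sets no formal hypotheses. The rule is the same in every arm and can only add TEAEs. That last point is only partly reassuring, because an extra TEAE on placebo can hide a difference. Unimputed listings would let a reader find a wrong case, but would not correct the table.

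A reader might also infer that medicines are wrongly classed as concomitant. The protocol does collect medicines "used by the patient within 30 days prior to the Screening visit should be entered on the Concomitant Medications eCRF", so some stopped before dosing will be on file. The documents do not support that inference: SAP 13.2 depends on use after first dose, which an imputed start does not create.

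**Conclusion.** The point holds for adverse events, as a minor defect. The start-date rule has no stop-date check. Taken literally with SAP 15.1, it can place an event's onset after its own end and count the event as treatment-emergent.

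The number affected cannot be estimated, because the documents give no frequency of partial dates. It is likely to be few, possibly none. The shift of 11 or 17 points per record assumes planned arm sizes with every subject dosed, and a subject with no other TEAE. The 41% to 64% range (day missing) also rests on the uniformity assumptions above.

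It would be too strong to say that affected records are certain to be misclassified, since SAP 10.1 allows a kinder reading. For medicines there is no stated error, only a possible ambiguity if a program tests the imputed start alone.

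**What to change.** Add to both bullets of SAP 10.1.1:

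*If the stop date (complete, or as imputed under 10.1.2) is before the date used in the calculation, the start date is not moved to that date; it is imputed as the first day of the known month (or year), and the record is classed as pre-treatment.*

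Keep the existing rule for all other partial dates. A later worsening is not lost, because Protocol 10.5.3 requires a persistent event that becomes more severe to be recorded again. The same sentence removes the possible ambiguity for medicines.

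The cost is this addition to the SAP and one condition in the derivation program. No new data are needed and nothing changes for subjects.
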